13.1.1 Neuroimaging

Cranial MRI

All patients must have a cranial MRI with and without gadolinium at diagnosis/prior to enrollment. If surgical resection is performed, patients must have pre-operative and post-operative cranial MRI with and without gadolinium. The post-operative brain MRI should be obtained within 72 hours of surgery. If patient has a biopsy only, post-operative cranial MRI is recommended but not required.

Spinal MRI

All patients must have a spine MRI with gadolinium obtained at diagnosis/prior to enrollment.

Note: If the spine study is performed for the first time after surgical resection or biopsy, it is recommended to be obtained with and without gadolinium.

13.1.2 Medications

- Corticosteroids: Patients with large tumors and those with non-communicating hydrocephalus may benefit from high doses of corticosteroids such as dexamethasone (0.25-1.0 mg/kg/day) in divided doses every 6-8 hours. Appropriate endocrine tests should be drawn in consultation with the pediatric endocrine consultant prior to initiating corticosteroid therapy.
- Anticonvulsants: The use of prophylactic anticonvulsants in patients with CNS germ cell tumors in typical locations such as the suprasellar and pineal regions is not encouraged. Seizures are rare following endoscopic third ventriculostomy or intraventricular tumor biopsy. Prophylactic anticonvulsants may be administered prior to craniotomies and corticectomies depending on institutional policy.

13.1.3 Hydrocephalus

- Most patients with pineal region tumors will present with a non-communicating hydrocephalus due to obstruction of flow at the level of midbrain through the aqueduct of Sylvius.
- A communicating hydrocephalus may arise as a consequence of diffuse leptomeningeal metastases. The management of hydrocephalus will relate to the severity of symptoms of raised intracranial pressure and the clinical response to corticosteroids.
- The preferable management for patients with a pineal region tumor and obstructive hydrocephalus is a third ventriculostomy at the time of endoscopic biopsy.
- The routine placement of a VP shunt is not recommended.

13.1.4 Tumor Sampling and Resection

See Section 3.2.2 regarding eligible diagnosis.

- It is highly desirable to first confirm the diagnosis on frozen section in the operating room and then to obtain sufficient tissue for flash freezing (biology studies) and formalin fixation (complete immunohistological characterization).
- Radical resection for reduction of tumor burden is discouraged given the rapidity with which responses are expected with either radiation therapy or chemotherapy.

13.1.5 Intra-operative CSF sampling

- For patients undergoing an endoscopic procedure, it is highly desirable that intraventricular CSF sample to be obtained prior to biopsy and sent for cytology, hCG and AFP. The ventricular CSF should be obtained before fluid is instilled for irrigation.
- Lumbar CSF should be obtained (within 10-14 days after surgery if applicable) for cytopathology prior to enrollment unless medically contraindicated.

13.2 **Operative Management**

13.2.1 Endoscopy

- It is recommended that the endoscope be used for intraventricular tumor biopsy and for performance of a third ventriculostomy, if needed.
- Normal sized ventricles do not preclude the use of the endoscope for tumor biopsy if stereotactic guidance is available. The endoscope should be coupled to the frameless navigation system. The visual documentation of seeding, undetectable at the level of sensitivity of neuroimaging, will be documented, but will not alter radiation treatment.

13.2.2 Other Operative Approaches

It is recognized that some tumors may not be easily biopsied by endoscopic techniques and alternate approaches may be appropriate, depending on the anatomy of the tumor and institutional expertise. These include the following:

- Stereotactic needle biopsy
Image-guided frame-based techniques are preferred at some sites for appropriately selected tumors. Careful planning of the trajectory is essential to minimize the risk of injury to deep venous and arterial structures.
- Transphenoidal procedures
The transphenoidal approach may be the preferred method to biopsy a isolated suprasellar tumor, especially if a radical resection is not required. The morbidity of this approach is less than a craniotomy.

- Open craniotomy
If the above techniques are not deemed feasible or fail to yield diagnostic tissue, an open craniotomy would be appropriate as a means for establishing the diagnosis of a germ cell tumor. The operative approach would be determined by the lesion location and geometry.

13.2.3 Ancillary Procedures

- External ventricular drain (EVD)
In some circumstances an EVD may be necessary for monitoring intracranial pressure or temporary control of hydrocephalus.
- Septostomy
If the tumor is producing hydrocephalus by obstructing a lateral ventricle at the level of the foramen of Monro, a third ventriculostomy may not be possible. In such cases, a septostomy may allow a communication to be established between the two lateral ventricles and permit a tumor biopsy at the same procedure.

13.2.4 Internal Shunts

The routine use of permanent internal shunts is discouraged. However, a ventriculo-peritoneal shunt may be necessary in specific circumstances when a third ventriculostomy is not feasible or contraindicated, i.e., in the presence of tumor deposits on the floor of the third ventricle or communicating hydrocephalus.

13.3 **Management of Complications**

- Peri-surgical complications include hemorrhage, infection, seizures, and neurological injury.
- Significant complications will delay the implementation of adjuvant therapy and may preclude protocol eligibility.
- The patient must be ready to begin protocol therapy within 31 days of surgery. Readiness assumes significant recovery from peri-operative complications and absence of any wound dehiscence, CSF leakage, uncontrolled hydrocephalus or uncontrolled life-threatening endocrine deficiency.

13.4 **Second-Look Surgery**

- The presence of residual or progressive disease after the completion of induction chemotherapy in patients following 4 or 6 (NGGCT) cycles of chemotherapy warrants consideration of a “second-look” surgical procedure.
- All differential diagnostic concerns must be considered to include: a non-germinomatous germ cell component, mature teratoma, a non-protocol tumor and scar/fibrosis.
- Appropriate management will depend on narrowing this differential. An open craniotomy may be the preferred procedure since a radical resection of residual tumor may be therapeutic.⁴

14.0 IMAGING STUDIES REQUIRED AND GUIDELINES FOR OBTAINING

Timing of protocol therapy administration, response assessment studies, and surgical interventions are based on schedules derived from the experimental design or on established standards of care. Minor unavoidable departures (up to 72 hours) from protocol directed therapy and/or disease evaluations (and up to 1 week for surgery) for valid clinical, patient and family logistical, or facility, procedure and/or anesthesia scheduling issues are acceptable per COG administrative Policy 5.14 (except where explicitly prohibited within the protocol).

14.1 Timing of MRIs

Cranial MRI

All patients must have a cranial MRI with and without gadolinium at diagnosis/prior to enrollment. If surgical resection is performed, patients must have pre-operative and post-operative cranial MRI with and without gadolinium. The post-operative brain MRI should be obtained within 72 hours of surgery. If patient has a biopsy only, post-operative cranial MRI is recommended but not required.

Spinal MRI

All patients must have a spine MRI with gadolinium obtained at diagnosis/prior to enrollment.

Note: If the spine study is performed for the first time after surgical resection or biopsy, it is recommended to be obtained with and without gadolinium.

To document localized disease, standard cranial MRI with and without gadolinium and a spine MRI with gadolinium must be performed at the following time points:

Brain

- Pre-operative and Post-operative (if applicable)
- Baseline (Prior to enrollment)
- After Cycles 2 and 4 of Induction
- Completion of Induction
- After Second-Look Surgery (if done)
- End of Therapy

Spine

- A spine MRI obtained preoperatively can be obtained with gadolinium only. If the spine study is performed for the first time post-op, it is recommended to be performed without and with gadolinium
- Completion of Induction
- End of therapy

14.2 MRI Guidelines for Brain/Spine Tumors

For recommended brain/spine imaging (1.5 Tesla), required and optional sequences and technical details, see the COG CNS Imaging Guidelines posted on the COG member website at:

https://members.childrensoncologygroup.org/_files/reference/RefMaterial/COGCNSImagingGuidelines6_4_10.pdf

14.3 Tumor Response Assessment

For the response assessments, MRI scans obtained at the time-points during protocol therapy (see Section 10.4) will be compared to the baseline MRI scan. **Exception:** In cases of progressive disease, the reference scan should be the MRI with the smallest product observed since the start of treatment).

14.4 Retrospective Central Review

A retrospective central review of imaging will be performed for all patients enrolled on ACNS1123. Results of the retrospective review will not be returned to the site. Submit the following studies that have not already been submitted for the RT on-treatment review with their corresponding reports for central review at the completion of treatment or when the patient is removed from protocol therapy or at the time of progressive disease/recurrence.

Brain

- Baseline
- Pre and Post Operative scan (if applicable)
- End of Induction
- Post Second-look Surgery
- End of Therapy
- Progressive Disease/Recurrence

Spine

- Progressive Disease/Recurrence

15.0 RADIATION THERAPY GUIDELINES

Timing of protocol therapy administration, response assessment studies, and surgical interventions are based on schedules derived from the experimental design or on established standards of care. Minor unavoidable departures (up to 72 hours) from protocol directed therapy and/or disease evaluations (and up to 1 week for surgery) for valid clinical, patient and family logistical, or facility, procedure and/or anesthesia scheduling issues are acceptable per COG administrative Policy 5.14 (except where explicitly prohibited within the protocol).

Radiation Therapy (RT) can only be delivered at approved RT facilities (COG administrative policy 3.9).

15.0 General Guidelines

The indications for radiation therapy on this protocol will be based on response to induction chemotherapy. All patients will receive radiotherapy after induction chemotherapy, unless recommended to undergo second surgery. If second-look surgery is performed, radiation therapy will be performed following the surgery. The radiation dose and fields will be based on both histology and response to induction chemotherapy or results from second surgery. This study specifies a 5 mm clinical target volume margin and mandates the use of CT-MR registration to define the target volumes. The allowed treatment methods are restricted to conformal or intensity-modulated radiation therapy using photons or proton beam therapy and electronic data submission is required.

15.0.1 Treatment Planning Specifics

The guidelines for this study were developed by COG radiation oncology investigators and approved by the radiation oncology discipline committee. This study stratifies NGGCT to Stratum 1 and Germinoma to Stratum 2. Both strata include whole ventricular irradiation followed by boost irradiation of the primary site. The prescribed doses to the ventricular and boost volumes are fixed for Stratum 1 and vary according to response for Stratum 2. The whole ventricular volume should be contoured according to an atlas approved by the radiation oncology committee.

15.0.2 Required Benchmark and Questionnaires

Radiation therapy will be administered using protons or photons. Required photon methods include 3D-conformal radiation therapy (3D-CRT) and intensity modulated radiation therapy (IMRT). Centers participating in this protocol using 3D-CRT are required to complete the 3D benchmark; those using IMRT must complete the IMRT questionnaire and benchmark or phantom and those using protons must complete the proton benchmark and questionnaire. All centers participating in this protocol must complete the IROC RI (QARC) CT/MR image fusion benchmark. Benchmark materials and questionnaires may be obtained from the IROC RI (QARC) (www.qarc.org) and must be submitted before patients on this protocol can be evaluated. For information regarding the IMRT phantoms, please contact the RPC (<http://rpc.mdanderson.org/rpc>).

15.0.3 Guidelines and Requirements for the Use of IMRT

Investigators using IMRT will be required to comply with the guidelines developed for the use of IMRT in National Cancer Institute sponsored

cooperative group trials. These guidelines are available through www.qarc.org. These guidelines require that the protocol explicitly state their requirements and methods for localization and immobilization; the use of volumetric imaging; target and organ motion management; nomenclature, definitions and rationale for targets and organs at risk; target volume coverage and normal tissue dose constraints; effects of heterogeneity in tissues; and quality assurance.

15.0.4 Guidelines and Requirements for the Use of Proton Beam Therapy

Proton therapy may be used to deliver radiation therapy on this protocol. The proton therapy method will be limited to passive scattering and uniform scanning. Investigators using proton beam radiation must comply with the Advanced Technology Consortium proton therapy guidelines available through www.qarc.org. These guidelines specify the following for the participating institution: both passive and scanned beams may be used, but the Radiologic Physics Center must review and credential the specific beam line delivery parameters. Dose reporting will be in Gy (RBE). Radiation doses shall be prescribed protocol specified definitions for gross (GTV) and clinical (CTV) target volumes. For set-up uncertainties and target motion, additional margin, smearing, range of modulation will be added on a per beam basis. The proton institution is required to participate in on-site and remote review according to COG guidelines.⁷⁹⁻⁸¹

15.1 **Indications for Radiation Therapy**

15.1.1 Stratum 1

Stratum 1 patients with NGGCT enrolled on this protocol will receive 6 cycles of induction chemotherapy. If there is a CR by neuroimaging or PR with marker normalization following chemotherapy, radiation therapy will follow the 6th cycle of chemotherapy. If there is PR, SD or PD to chemotherapy, second-look surgery is recommended. If surgery results in a PR or CR and tumor marker normalization, radiation therapy will follow surgery. If there is <PR or positive markers after 6 cycles of induction or if there is residual viable tumor (except mature teratoma) at the time of second-look surgery, the patient will be removed from protocol therapy.

15.1.2 Stratum 2

Stratum 2 patients with Germinoma enrolled on this protocol will receive 4 cycles of induction chemotherapy. If there is a CR or CCR to chemotherapy, radiation therapy will follow the 4th cycle of chemotherapy. If there is PR, SD, or PD after chemotherapy, second surgery is highly recommended. If mature teratoma or scar/fibrosis/non-viable tumor is found on second-look surgery, then radiation therapy will follow surgery. If surgery identifies viable tumor other than mature teratoma, the patient will be removed from protocol therapy. Patients with positive markers after induction chemotherapy will be removed from protocol therapy.

If there is SD or PR after chemotherapy (> 0.5 cm (suprasellar) or > 1 cm (pineal) but ≤ 1.5 cm residual) and second-look surgery is not performed, radiation therapy will follow and a higher dose to the ventricular volume will be administered with a subsequent increase in the total dose to the primary site. If

second-look surgery is not performed and patients do not meet criteria for at least PR with ≤ 1.5 cm residual disease, patients will be off protocol therapy.

15.2 Timing

15.2.1

It is recommended that all patients be seen in consultation by a radiation oncologist at the time of study enrollment. The purpose of the consultation is to participate in staging and to review the adequacy of the initial diagnostic imaging studies that will be used for subsequent RT planning.

15.2.2

There are no contraindications to radiation therapy. Patients taking phenytoin should be weaned and/or switched to a different anticonvulsant as soon as feasible.

15.2.3 Stratum 1 (NGGCT)

- If CR/PR after 6 cycles of induction chemotherapy, radiotherapy should commence within 3 weeks of recovery from last chemotherapy (Day 21) and no later than 6 weeks after the first day of the last chemotherapy cycle or the patient will be removed from protocol therapy (See Section 8.1).
- If PR, SD or PD after 6 cycles of induction chemotherapy, radiotherapy will not begin until after second-look surgery. Radiotherapy must begin within 31 days after surgery. If the patient has positive markers or $<$ PR after second-look surgery, they will be removed from protocol therapy. If radiotherapy is not initiated within 31 days after surgery, the patient will be removed from protocol therapy.

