8.0 CRITERIA FOR REMOVAL FROM PROTOCOL THERAPY AND OFF STUDY CRITERIA

8.1 Criteria for Removal from Protocol Therapy

- a) Progressive disease with increasing markers during Induction chemotherapy.
- b) NGGCT (Stratum 1) patients with positive markers at the end of Induction chemotherapy or who have < PR after induction chemotherapy.
- c) NGGCT (Stratum 1) patients with < PR after second-look surgery or any viable tumor (except mature teratoma) after second-look surgery
- d) NGGCT (Stratum 1) patients who are unable to undergo second-look surgery due to safety or other reasons and do not meet criteria for CR/PR (imaging and tumor markers).
- e) Germinoma (Stratum 2) patients with PD and positive markers at the end of Induction chemotherapy.
- f) Germinoma (Stratum 2) patients who are unable to undergo second-look surgery due to safety concerns and they do not meet the criteria for at least PR with ≤ 1.5 cm residual disease without second-look surgery.
- g) Germinoma (Stratum 2) patients with any viable tumor (except mature teratoma, fibrosis, scar or non-viable tumor) after second-look surgery
- h) Refusal of further protocol therapy by patient/parent/guardian.
- i) Completion of protocol therapy.
- j) Physician determines it is in patient's best interest.
- k) Development of a second malignancy.
- l) Patient is enrolled but rechecked labs are outside the limits of eligibility prior to starting therapy. (See [Section 3.2](#))
- m) Radiotherapy cannot be initiated within 6 weeks after Day 1 of the last cycle of Induction chemotherapy or within 31 days after second-look surgery. (See [Sections 15.2.3](#) and [15.2.4](#)).
- n) Progressive disease with positive or increasing markers at the end of Induction chemotherapy, following second-look surgery or during radiation therapy.

Patients who are off protocol therapy are to be followed until they meet the criteria for Off Study (see below). Follow-up data will be required unless consent was withdrawn.

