15.10.1 On-treatment Review

Within three days of the start of radiotherapy, the following data for the whole ventricle fields shall be submitted for on-treatment review. Boost data must be submitted prior to the start of the boost, but preferably should be submitted with the whole ventricle data at the start of radiotherapy:

Treatment Planning System Output:

- RT treatment plans including CT, structures, dose, and plan files. These items are included in the digital plan.
- Dose volume histograms (DVH) for the composite treatment plan for all target volumes and required organs at risk. When using IMRT, a DVH shall be submitted for a category of tissue called “unspecified tissue.” This is defined as tissue contained within the skin, but which is not otherwise identified by containment within any other structure. DVHs are included in the digital plan.
- Digitally reconstructed radiographs (DRR) for each treatment field. Please include two sets, one with and one without overlays of the target volumes and organs at risk. When using IMRT, orthogonal setup images are sufficient.
- Treatment planning system summary report that includes the monitor unit calculations, beam parameters, calculation algorithm, and volume of interest dose statistics.

Supportive Data:

- Copies of the operative reports for each surgical procedure.
- Copies of the prechemotherapy and postchemotherapy MRI scans and radiology reports utilized in defining the initial clinical target volume and the local boost volume.
- Pre-operative and post-operative cranial neuroimaging and radiology reports for each surgical procedure including second surgery after induction chemotherapy.
- Post-chemotherapy (pre-RT) neuroimaging and radiology reports when no second surgery was performed.
- Documentation of an independent check of the calculated dose when IMRT is used.
- If the recommended doses to the organs at risk are exceeded, an explanation should be included for review by the QARC and the radiation oncology reviewers.
- Proton therapy: smearing radius of the compensator, set-up margin (SM) and PTV margin for each treatment beam.

Forms:

- RT1/IMRT Dosimetry Summary Form (QARC).
- Proton Dosimetry Summary Form (QARC).

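### Section 15.2.3 bars radiotherapy in Stratum 1 partial response until second-look surgery, although its own first bullet and the rest of the protocol let a marker-negative, unoperated PR patient proceed

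*Combined protocol and SAP*

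**What the plan says.** Section 15.2.3 has two bullets for Stratum 1, and both name PR.

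- **Bullet 1:** "If CR/PR after 6 cycles of induction chemotherapy, radiotherapy should commence within 3 weeks of recovery from last chemotherapy (Day 21"). It adds a limit of 6 weeks from the first day of the last cycle, with removal from protocol therapy if the limit is missed. It sets no condition about surgery.
- **Bullet 2:** "If PR, SD or PD after 6 cycles of induction chemotherapy, radiotherapy will not begin until after second-look surgery". Then: "Radiotherapy must begin within 31 days after surgery", again with removal if missed.

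Other sections on PR after induction in Stratum 1:

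- **Section 15.1.1:** "If there is a CR by neuroimaging or PR with marker normalization following chemotherapy, radiation therapy will follow the 6th cycle of chemotherapy". Surgery in PR is then recommended.
- **Section 4.1:** patients in CR or PR go on to radiotherapy. Surgery is strongly recommended for PR, SD or PD with normal markers, and unoperated patients come off only if they fall short of CR or PR.
- **Schema 1 footnote:** surgery is advised but expressly optional, with the same rule for unoperated patients.
- **Section 8.1(b):** removes "patients with positive markers at the end of Induction chemotherapy or who have < PR after induction chemotherapy". Section 8.1(d) removes unoperated patients only when CR or PR is not met.
- **Section 15.0 General Guidelines:** "All patients will receive radiotherapy after induction chemotherapy, unless recommended to undergo second surgery". The next sentence is conditional: "If second-look surgery is performed, radiation therapy will be performed following the surgery".
- **Section 8.1(m):** lists the 6-week and 31-day limits joined by *or*, without saying who falls under which.

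**The concern.** An unoperated PR patient with normal markers must start radiotherapy by 6 weeks under bullet 1 and may not start at all under bullet 2. A site that follows bullet 2 to the letter must either arrange an operation or let the 6-week limit pass and remove the patient.

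This affects the analysis as well as conduct. Section 9.1 builds the Stratum 1 primary set from eligible patients who receive the reduced radiotherapy. Those who do not are only counted and reported. Two sites reading different sections could therefore place identical patients inside and outside the primary set.

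The secondary point concerns PR patients who are operated on after cycle 6. Bullet 1 does not say that its 6-week limit gives way to the 31-day limit of bullet 2.

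**Working it through.** **1. The plan's own figures.** Section 9.3.1 uses an exact binomial rule: 77 patients, success if at least 69 are progression free at 3 years.

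- P(X ≥ 69 | n = 77, p = 0.82) = 0.0492, as stated.
- P(X ≥ 69 | n = 77, p = 0.93) = 0.911, as stated.

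Nothing below changes these.

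**2. Unoperated PR with normal markers: may radiotherapy start?**

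| Place | Answer |
|---|---|
| 15.2.3 bullet 1 | Yes, with a time limit |
| 15.2.3 bullet 2 | No, surgery first |
| Schema 1 footnote | Yes, surgery optional |
| 4.1 | Yes, surgery recommended |
| 8.1(d) | Stays on protocol therapy |
| 15.1.1 | Yes, after cycle 6 |
| 15.0 General Guidelines | Unclear |

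The General Guidelines exempt patients for whom surgery is recommended, and Section 4.1 recommends it in PR. That combination lends bullet 2 some support. The conditional sentence that follows points the other way.

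Two further places fit the *yes* reading but prove little. Table 15.6.2 has a CR/PR row separate from its after-surgery rows, but that row does not mention surgery. Section 15.10.1 asks for "neuroimaging and radiology reports when no second surgery was performed", but this also covers CR and Stratum 2.

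**3. The two limits for PR operated on after cycle 6.** Six weeks after Day 1 of the last cycle is Day 1 + 42 = Day 43. Section 7.1 puts the end-of-induction evaluation at Day 21 to 35. If surgery took place on the evaluation day:

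- Day 21: the 31-day limit is 21 + 31 = Day 52, which is 9 days after Day 43.
- Day 35: the 31-day limit is 35 + 31 = Day 66, which is 23 days after Day 43.

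The full 31 days fit within Day 43 only if surgery is done by 43 − 31 = Day 12, before the evaluation that defines PR. If bullet 1 also bound these patients, 43 − 21 = 22 days down to 43 − 35 = 8 days would remain after same-day surgery. The scheduling tolerance of 72 hours (one week for surgery) does not bridge a gap of 9 days.

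**4. Exposure.** Section 9.3.1 reports PR in 17 of 79 localized reference-study patients.

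- Share: 17/79 = 21.5% (exact 95% CI 13.1% to 32.2%).
- Eligible Stratum 1 patients needed: 77 ÷ (49/79) = 124.1; Section 9.2.3 plans about 125.
- PR patients expected: 125 × 17/79 = 26.9, about 27 (interval 16 to 40).

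The documents do not split PR into operated and unoperated patients, so neither part of the point can be sized alone.

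**The case against.** The strongest reply is that the protocol, read as a whole, already settles the question. Section 15.1.1 governs indications, the Schema says surgery is optional, and Section 8.1(d) keeps unoperated PR patients on therapy. Section 15.2.3 is only a timing section. This stands as evidence of intent, and it is why the expected loss is zero where sites read across sections. It does not remove the conflict: bullet 2 is an unqualified rule in the section that sites consult for timing, and it contradicts the bullet directly above it.

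A reader might go further in three ways that the documents do not support.

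- **Two incompatible deadlines for operated PR.** They are not incompatible. Both are upper limits, and starting by the earlier one meets both. The *or* in Section 8.1(m) reads naturally as one limit for unoperated and one for operated patients. What remains is that the assignment is never stated: bullet 1 points to Section 8.1, and Section 8.1(m) points back to Section 15.2.3.
- **About 27 of the 77, or 35% (17 of 49).** The 77 are by definition patients who received the reduced radiotherapy, so nobody removed earlier can be among them. The right base is eligible enrolled patients.
- **A loss of power.** The plan accrues until 77 evaluable patients are reached, and the decision rule is fixed on that number.

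**Conclusion.** The point holds. For marker-negative PR in Stratum 1, bullet 2 of Section 15.2.3 is wrong as written, because it makes a condition of surgery that the rest of the protocol only recommends. The exemption in the Section 15.0 General Guidelines adds to the ambiguity. The unassigned 6-week and 31-day limits are a lesser gap in drafting.

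The size is exposure of about 27 of 125 eligible patients, assuming the reference-study response mix. It may be smaller. Section 10.4 counts residual disease up to 0.5 cm (suprasellar) or 1 cm (pineal) as CR, while Section 2.1.3 describes CR in the reference study as complete, so some of the 17 could be CR here. The documents do not say how many; each one reclassified would lower the count by 125/79, about 1.6 patients. This is an operative error worth correcting, not a fault in the statistical design.

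**What to change.** Change four pieces of text.

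- **15.2.3 bullet 1:** limit it to CR or PR with normal serum and CSF markers after 6 cycles and no second-look surgery after cycle 6, whether or not surgery was done during induction. Keep the 3-week start, the 6-week limit and removal.
- **15.2.3 bullet 2:** for SD or PD after 6 cycles, radiotherapy waits for second-look surgery. Where such surgery is done after cycle 6 for PR, SD or PD, radiotherapy starts within 31 days of that operation and the 6-week limit does not apply. Keep the existing removal rules.
- **15.0 General Guidelines:** make the exemption depend on second-look surgery actually performed after completion of induction, or on removal under Section 8.1, instead of on a recommendation.
- **8.1(m):** state that the 6-week limit applies to patients without post-induction surgery and the 31-day limit to those with it.

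The words *after cycle 6* matter. Section 4.1 allows second-look surgery during induction, with therapy then continued as planned. A bullet 1 limited simply to unoperated patients would leave such a patient in CR under neither bullet, and would give one in PR a 31-day limit that may already have expired. Section 15.2.4 already separates operated from unoperated patients for Stratum 2 and can serve as the model.

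The cost is an amendment to wording and a site notice. No procedures, data or patients are added.
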